## 4.6 Multiple Comparisons

The Multiple Comparison Procedure – Modeling (MCP-Mod) method will be used to assess the primary endpoint. Details of the method is provided in Section 6.1 below.

A hierarchical (i.e., simple fixed sequence testing) testing strategy will be used to protect the overall type I error rate when testing the primary efficacy endpoint with the key secondary efficacy endpoint.

No adjustment for multiplicity will be performed for testing the non-key secondary and exploratory endpoints.

## 4.7 Data Derivations and Transformations

The following derivations will be used in this study:

Study Day:

- Equal to (date of assessment date of first dose + 1) for assessments done on or after date of first dose
- Equal to (date of assessment date of first dose) for assessments before date of first dose

Baseline Observation: the last non-missing value prior to first study drug administration.

Duration: end date – start date +1; measured in days.

Change from Baseline: post-baseline value - baseline value

Percent Change from Baseline: (post-baseline value - baseline value) / baseline value x 100

## 5 STUDY PATIENTS

## 5.1 Disposition of Patients

A table of frequency counts of all subjects who are enrolled, randomized, treated, and in each analysis population will be provided. Frequency counts and percentages of subject disposition including study completion status and reasons for early termination will be tabulated. A subject

#### CONFIDENTIAL

listing will be provided.

## 5.2 Protocol Deviations

Distribution of the types of protocol deviations and the number of subjects that deviate from the protocol will be tabulated by treatment group for the FAS. Protocol deviations will also be tabulated by severity (e.g., minor or major). A listing of all deviations will be provided.

## 5.3 Demographic Characteristics

Descriptive statistics will be used to summarize the demographic characteristics (age, sex at birth, self-identified gender, race, ethnicity, and baseline height, weight and BMI) by treatment group and overall, for the FAS and PPS populations. A listing of demographic characteristics will be provided.

## 5.4 Baseline Characteristics

Baseline values of HAM-A Total Score, MADRS Total Score, CGI-S, PGI-S, PSQI Global Score, SDS Total Score, and the proportion of subjects with sexual dysfunction according to the ASEX Total Score will be summarized for the FAS and PPS populations. The duration (in days) from the time of GAD diagnosis to study drug administration will be reported. A listing of baseline characteristics will be provided.

## 5.5 Medical History

All medical conditions and surgical procedures will be classified by system organ class (SOC) and preferred term (PT) using the Medical Dictionary for Regulatory Activities (MedDRA) version 24.1. The number and percent of subjects with each medical condition and surgical procedure will be presented for each SOC and PT by treatment group and overall, for the FAS and PPS populations. A listing of subject medical history will be provided.

## 5.6 Psychiatric History

All psychiatric conditions will be classified by system organ class (SOC) and preferred term (PT) using the Medical Dictionary for Regulatory Activities (MedDRA) version 24.1. The number and percent of subjects with each psychiatric condition will be presented for each SOC and PT by treatment group and overall, for the FAS and PPS populations. A listing of subject psychiatric history will be provided.

## 5.7 Prior and Concomitant Medications, Psychiatric Medications and Non-drug Treatments

Prior and concomitant medications and psychiatric medications taken for GAD will be coded using World Health Organization (WHO) drug classifications, version March 2022 B3. Non-drug treatments will be coded using the Medical Dictionary for Regulatory Activities (MedDRA).

Prior medications are defined as medications that ended prior to the date of first dose of study drug administration (Day 1). Concomitant medications are defined as medications that started at any time but ended on or after the date of first dose (Day 1), including those that are ongoing at study completion. In the case of a missing or partial end date, in order to determine whether a medication is prior or concomitant, the following conservative imputation rule will be used: the unknown

portions of a medication end date will be imputed to the latest possible day or month. The imputed medication date will then be compared with the date of first dose to determine if the medication is prior or concomitant.

The number and percent of subjects using prior medications and concomitant medications will be tabulated by Anatomical, Therapeutic, and Chemical (ATC) Level 2 and by preferred name. Prior medications will be summarized separately from concomitant medications and will be reported by treatment group and overall, for the FAS and PPS populations. A subject listing of all prior and concomitant medications will be provided.

Psychiatric medications taken for GAD will be summarized by ATC Level 2 and preferred name and presented by treatment group and overall. Prior psychiatric medications will be summarized separately from concomitant psychiatric medications for the FAS and PPS populations. A subject listing of all psychiatric medications taken for GAD will be provided.

Non-drug treatments will be summarized by system organ class (SOC) and preferred term (PT) by treatment group and overall. Prior non-drug treatments will be summarized separately from concomitant non-drug treatments. A subject listing of all non-drug treatments will be provided.

## 5.8 Neuropsychiatric Examination

The Neuropsychiatric examination will be performed at Baseline, Day 1, and all subsequent visits including End of Study. The examination at Baseline will establish a standard comparison for possible acute and lasting effects of the study drug. A subject listing by visit will be provided.

## 5.9 Dosing Release Checklist

The Dosing Release Checklist will, at a minimum, be performed approximately 8 and 12 hours post-dose to ascertain if the subject meets DSM-5 criteria for Hallucinogen Intoxication. Subjects will be assessed hourly at 9, 10, and 11 hours post-dose until all release criteria are met. A summary of the number and percentage of subjects meeting release criteria at each hourly time point will be provided. A subject listing by time point will be provided.

## 6 EFFICACY ANALYSIS

All efficacy analyses, primary and secondary, will be carried out on the FAS population. Where noted, additional analyses on the PPS population may be included.

## 6.1 Primary Efficacy Endpoint and Analysis

The primary efficacy endpoint is change from Baseline to Week 4 in HAM-A Total Score. The MCP-MOD method (Bretz 2005; Pinheiro 2014) will be used to assess the primary endpoint to investigate the dose-response relationship for the 4 doses levels of MM-120 versus placebo. The analysis of the primary endpoint using MCP-MOD will be performed on the FAS population. A sensitivity analysis will be performed on the PPS population.

The HAM-A consists of 14 items that encompass both psychological and somatic symptoms of anxiety. The HAM-A takes about 20 minutes to administer and will be completed by a central rater. The central rater will assess the extent to which the subject displays each given criterion and give a rating on a scale of 0-4, where 4 represents the most severe symptoms. The HAM-A Total Score will be calculated as the sum of the 14 items and will range from 0-56. Higher Total Scores

indicate increased severity of symptoms.

## 6.1.1 Handling of Missing Data and Potentially Biased Values

Missing data for the primary endpoint will be imputed using a multiple imputation approach assuming that the missingness mechanism can be retrieved from observed data. The imputation model will include the treatment group and the longitudinal sequence of HAM-A Total Score. Imputations will be performed 20 times using SAS PROC MI with the fully conditional specification (FCS) method.

For intercurrent events (IEs) the following methods will be used:

- The data recorded after the IE will be set to missing and imputed under a Missing Not at Random (MNAR) assumption by borrowing information from the placebo arm subjects (reference-based imputation) for the following:
  - Concomitant/prohibited medications that meet the threshold for impact = "Yes" during the impact assessment will be considered as the IE. Any observations after such an IE will be set to missing and will be imputed using the MNAR assumption.
- Available data will be used; missing data will be imputed under a Missing at Random (MAR) assumption, borrowing information from subjects in the same treatment arm for the following:
  - For IEs leading to study discontinuation due to other reasons
  - IEs related to the COVID-19 pandemic.

For missing data not due to IEs the imputation will be performed based on MAR assumption.

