The response data in each imputed data set, including relevant covariates, will be used to fit the models in the candidate set. The estimated dose-response will be derived by using model averaging methods on a subset of candidate models, for which the associated contrast tests are statistically significant. The  $\leq$  3 models with the largest t-statistics  $\geq$  C0.05 as calculated above will be selected as the basis for the model averaging.

Dose

Model averaging will be carried out for each imputed dataset, and the resulting mean efficacy estimates, and CIs will be derived using the combination variance that accounts for the uncertainty of the imputed data using Rubin's combination rules. Comparisons between MM-120 doses and placebo will be simultaneously derived for the model averaged estimates together with the CIs reflecting the imputation procedure applied. The model-averaging-based estimates of the mean changes from Baseline to Week 4 for HAM-A Total Score within each dose group, and the mean

differences between MM-120 and placebo and their CIs will then be displayed.

Target dose selection (e.g., minimum effective dose [MED], EDp) will be based on the model change from Baseline to Week 4 for the HAM-A Total Score over the dose range studied. MED is defined as the lowest dose ensuring a clinically relevant and statistically significant improvement, MED = min{ $d \in (d_1, d_5) : f(d) > f(d_1) + \Delta$ }, where  $\Delta$  is the clinical relevance threshold. EDp is defined as the lowest dose that gives a certain percentage p of maximum effect  $\delta_{max}$ . EDp = min{ $d \in (d_1, d_5) : f(d) > f(d_1) + p\delta_{max}$ }. For this analysis, p will be set to 100%. The final choice of the target dose depends on the evaluation of the primary efficacy variable and other efficacy variables, as well as safety considerations.

The above will be repeated using only the model with the largest t-statistic  $\geq C_{0.05}$ .

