## 6.2 Key Secondary Efficacy Endpoint and Analysis

## 6.2.1 Key Secondary Endpoint

The key secondary endpoint is change from Baseline to Week 8 in HAM-A Total Score. Analysis of this endpoint will follow the same process as the primary endpoint described in Section 6.1. The outcome for this endpoint will be considered confirmatory, if in agreement with the primary endpoint outcome and provided that the null hypothesis is rejected for the primary outcome. This gatekeeping function of the primary outcome allows for no adjustment of alpha level for multiplicity of testing.

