## 9 SAMPLE SIZE AND POWER CALCULATIONS

A total sample of 180 subjects, 36 per arm, is required to ensure a mean power >87% for an MCP-Mod Analysis rejecting the hypothesis of a constant dose-response curve using the multiple comparisons procedure (MCP), assuming a null placebo response, a maximum standardized effect of 0.6 within the doses range, and a common standard deviation within the dose arms, if a studywise one-sided type-1 error rate <0.05 is required.

The analysis assumes 4 doses of active medication (25, 50, 100 and 200  $\mu$ g freebase-equivalent) and placebo. The required sample size for each arm is 36 subjects.

The R package Dose Finding (https://CRAN.R-project.org/package=DoseFinding) has been used to estimate the sample size and corresponding power. The power for each model is estimated as shown Table 6.

Table 6	Power by Mode

Model	Power (%)
Sigmoid Emax (ED50, hill)	
10, 1	84.5
100, 5	90.7
100, 10	91.0
150, 10	89.9
Emax (D50 = 100)	83.2
Linear	85.0

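### SAP 6.1.1 sets 20 imputations and no seed, leaving avoidable Monte Carlo noise in the MCP-Mod verdict and, more often, in which models are averaged

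*SAP*

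**What the plan says.** SAP 6.1.1 gives the imputation method and number: "Imputations will be performed 20 times using SAS PROC MI with the fully conditional specification (FCS) method". It also gives the model: "The imputation model will include the treatment group and the longitudinal sequence of HAM-A Total Score". Protocol 10.2.2.1 leaves the details of the algorithm to the SAP, so SAP 6.1.1 is the full specification. Neither document states a seed, a Monte Carlo error check, a rule for raising the number of imputations, or an expected rate of missing Week 4 scores.

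SAP 6.1.2 uses the pooled results in three selections:
- **Step 1.** The largest of six contrast t-statistics is compared with one critical value, C0.05.
- **Step 2.** All candidate models are fitted in each imputed data set. Those averaged are at most three, chosen by largest t among those reaching C0.05.
- **Repeat.** "The above will be repeated using only the model with the largest t-statistic", again only if it reaches C0.05.

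For Week 8, SAP 6.2.1 says: "Analysis of this endpoint will follow the same process as the primary endpoint described in Section 6.1".

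**The concern.** Twenty imputations are commonly enough for one mean difference. Here the pooled quantities feed ranking and threshold rules, and a small change in a t-statistic can change a rule's outcome. The six contrasts are highly correlated, so their t-statistics often lie close together and a little imputation noise can reorder them.

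Two analysts who follow the SAP exactly on the same locked data, with different seeds, could average different models. Occasionally they could reach a different verdict on the primary test, which also gates the key secondary test (SAP 4.6 and 6.2.1).

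**Working it through.** **Inputs from the SAP.** m = 20 imputations (6.1.1). Six candidate curves at 0, 25, 50, 100 and 200 µg (6.1.2). 36 per arm, a maximum effect of 0.6 SD and a common SD (section 9). Section 9 also states the error rate: "one-sided type-1 error rate <0.05 is required".

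**Assumed, because the documents are silent.** Week 4 scores missing at random in 5%, 10%, 20% or 30%, half of those also lacking Week 2. Correlation 0.6 among post-baseline changes and -0.3 with baseline. True curve sigmoid (100, 5), Emax or linear.

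**1. The plan's own figure.** With optimal contrasts and a multivariate-t critical value of 2.042 (df 175), power is 84.6, 90.7, 91.0, 89.9, 83.2 and 85.1%. SAP Table 6 gives 84.5, 90.7, 91.0, 89.9, 83.2 and 85.0%, with mean 524.3/6 = 87.4%. The setup therefore matches the plan's.

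**2. Why the ranking is fragile.** With equal arms, the correlation of two optimal contrasts is the correlation of the two curve shapes over the five doses. It is 0.9996 for sigmoid (100, 5) with (100, 10), 0.977 for sigmoid (100, 5) with linear, and 0.948 for Emax with linear.

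**3. Size of the noise by hand.** Let W be the within- and B the between-imputation covariance. Rubin's rules give T = W + (1 + 1/m)B, and each t is c′Q̄ / √(c′Tc), where c is the contrast and Q̄ holds the pooled means. Let λ be the between-imputation share of the contrast's variance. The seed-to-seed SD of t has two parts:
- from the numerator, about √(λ/m);
- from estimating B, about t × ½ × λ × √(2/(m − 1)).

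For a typical t, take the linear curve with scaled shape 0, 0.125, 0.25, 0.5, 1. Its sum of squared deviations is 0.625, so t ≈ √36 × 0.6 × √0.625 = 2.85. At 20% missing the simulated λ is 0.146. With m = 20 the parts are √(0.146/20) = 0.085 and 2.85 × 0.5 × 0.146 × √(2/19) = 0.067, and together √(0.085² + 0.067²) = 0.109. The simulation below gives 0.113-0.118.

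**4. Simulation.** There were 200 trials per scenario, with Bayesian regression imputation, ANCOVA, Rubin pooling and a fixed critical value of 2.043 (df 174). For each trial, 5,000 imputations were split into independent sets of 20, 100 or 500. Entries are ranges over the three true curves. Disagreement is the percentage of seed pairs on the same data that differ.

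| Missing | SD of max t, m = 20 | Significance: m = 20 / 100 / 500 | Averaged set: m = 20 / 100 / 500 | Averaged set by family, m = 20 | Top family, m = 20 |
|---|---|---|---|---|---|
| 5% | 0.045-0.047 | 0.6-1.7 / 0.1-1.3 / 0-1.0 | 4.7-7.5 / 1.8-3.9 / 1.1-2.2 | 2.9-5.1 | 3.1-4.2 |
| 10% | 0.070-0.073 | 0.9-2.3 / 0.2-1.4 / 0-0.6 | 10-11 / 4-5 / 1.4-2.0 | 6.7-7.9 | 6.9-7.5 |
| 20% | 0.113-0.118 | 1.8-3.2 / 0.7-2.0 / 0.1-0.9 | 18-20 / 9-10 / 4-5 | 12.0-14.7 | 8.3-11.6 |
| 30% | 0.152-0.160 | 3.1-3.8 / 1.5-2.0 / 0.4-1.6 | 23-27 / 12-13 / 5-6 | 15.7-19.7 | 13.5-16.1 |

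Families are sigmoid Emax, Emax and linear. In trials with max t within 0.15 of the critical value, seeds disagreed on significance in 11-40% at 5-20% missing. That rests on only 8-15 trials per scenario, so it is rough.

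Separate simulations at 5-20% missing gave 0.4-4.0% for significance, 6-20% for the averaged set and 2-12% for the top family.

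**5. Effect on the estimates.** Across two seeds at m = 20 (1,000 trials per scenario, 5-20% missing, trials significant under both, equal model weights, fits to pooled means), the averaged effect at the worst-affected dose moved by a median of 0.009-0.025 SD, 90th percentile 0.03-0.07 SD. The standard error of the 200 µg difference from placebo is about √(2/36) = 0.24 SD with complete data, so the median movement is about 4-10% of one standard error. In the single-model repeat, when the best family changed, the fitted effect at some dose moved by a median of about 0.11-0.16 SD, against the maximum effect of 0.6 SD.

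**The case against.** The case for leaving 20 imputations is substantial.

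- **Validity.** The between-imputation share of variance was about 4-22%, and Rubin's rules hold at m = 20. A reader might infer that the primary test is invalid or its error rate inflated. Nothing in the documents or the calculations supports that.
- **The main output is stable.** A reader might take 0.11-0.16 SD as the instability of the reported curve. It applies only to the single-model repeat, and only when the family changes. Averaging damps the rest. This stands.
- **What the seed selects.** A reader might infer that the seed decides which models are fitted. SAP 6.1.2 fits the whole candidate set; selection decides which are averaged. Four of the six candidates are sigmoid Emax, so if parameters are re-estimated, a swap among them may change nothing of substance. The family-level rates allow for this and are still not negligible.
- **Missing data may be few.** A single dose, the full analysis set's requirement for a post-baseline HAM-A, and a Week 4 window of Day 22 to 43 (SAP 4.3) all help. At 5% missing, the gain on significance from 500 imputations is about one percentage point or less. This stands.
- **Double programming.** SAP 4.1 requires matching outputs, which in practice needs a common seed or shared imputed data. That does not pre-specify the seed or reduce the noise.
- **Dose choice.** The seed does not choose the dose: SAP 6.1.2 also weighs other efficacy variables and safety.
- **Why 500?** No error criterion singles out that number, and 100 already roughly halves the disagreement. The exact figure is a judgement.

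**Conclusion.** The concern holds as a matter of Monte Carlo noise and reproducibility. With 20 imputations, no stated seed and 5-20% of Week 4 scores missing at random, two runs on the same data disagree:
- on significance in about 0.5-4% of trials, mainly near the threshold;
- on the candidate models averaged in about 5-20%, or about 4-15% by distinct family (lowest single scenario 2.9%);
- on the top-model family in about 2-12%.

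These figures depend on the assumed missing rate and correlations. They cover missing-at-random imputation only; the placebo-based imputation after medication events was not simulated. With 200 trials per scenario in the table, the small percentages are approximate. It is a free improvement, not a fault that undermines the analysis.

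**What to change.** In SAP 6.1.1, replace 20 with a much larger number of imputations, for example 500 or more, and state the seed. Apply both to the Week 4 and Week 8 MCP-Mod analyses. Going from 20 to 500 cuts the noise by a factor of about √(500/20) = 5. A fixed seed alone makes a run repeatable but leaves the result dependent on an arbitrary draw, so both changes are needed.

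The SAP addendum (section 1) says the primary endpoint has already been reviewed unblinded. If results from 20 imputations stand, report a disclosed large-m rerun showing whether it confirms the significance verdict and the selected models.

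The only cost is computing time. The estimand, the imputation model and the data do not change.

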6.10.1. Prohibited Medications, Supplements and Therapeutics

The use of medications, supplements and other therapeutics (over-the-counter or prescribed) for treating anxiety, depression or mood disorders are prohibited from Baseline (Visit 2) until End of Study (except if needed during Day 1/Dosing Session [Visit 3B], as noted in Table 5. Additionally, the use of other substances, supplements, etc. that may confound the results of the study are prohibited from Baseline (Visit 2) until End of Study (e.g., cannabis, cannabidiol [CBD], ginkgo biloba).

Subjects must also avoid starting, stopping or altering non-medicinal therapies from the time of providing informed consent until End of Study, as described in Section 5.2.3.

Any prohibited substance(s) being taken at the time of Screening (Visit 1) should be tapered prior to at Baseline (Visit 2), if safe for the subject, in the opinion of the Investigator; tapering

will be done with oversight from the study site designated physician and in accordance with information provided in Section 8.1.6.

Table 5 provides a listing of specific restrictions for concomitant therapy use during the course of this study, with any necessary washout periods or allowable conditions described. This table provides examples; however, it is not a comprehensive list of all restricted medications, supplements and other therapeutics. Consult the Sponsor's Medical Monitor or designee if there is any uncertainty regarding a subject's use of a particular drug, drug class, supplement or other therapeutic.

Subjects on prohibited medications, supplements or other therapeutics at the time of Screening (Visit 1) may taper off that substance (see Section 8.1.6) and participate in the study if the required washout conditions have been met. For prescribed medications to treat anxiety, depression or other mood disorders, the medication taper will be overseen by the study site designated physician based on acceptable local practice standards.

The final decision to continue or discontinue any medications/supplements/therapeutics that the subject is taking rests with the subject, the study site designated physician and/or the subject's primary care provider. However, the decision to have the subject receive study drug requires the mutual agreement of the Investigator, the Sponsor and the subject.

[figure not shown]
Clinical Study Protocol: MMED008

Table 5: Listing of Prohibited Medications, Supplements and Other Therapies

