10.2.2. Efficacy Analyses

10.2.2.1. Primary Estimand

The primary estimand quantifies the treatment effect of MM-120 at 4 weeks post-dose administration while accounting for intercurrent events (IEs) with potential confounding effects and IEs leading to study discontinuation prior to the 4-week assessment.

The following attributes describe the primary estimand:

- Population: As defined by the Inclusion/Exclusion criteria
- Endpoint: Change from Baseline to Week 4 in HAM-A Total Score
- Treatment of interest /the randomized treatment: 4 doses of MM-120 (25, 50, 100, or 200 µg free-base equivalent) or placebo as a single-dose treatment.
- Handling of IEs prior to HAM-A assessment at Week 4:
 - Intake or change in concomitant medications/therapies which have potential confounding effects per the impact assessment.
 - Intake of prohibited medications/therapies assessed as "Yes" per the impact assessment.
 - *Policy strategy:* Available data recorded after the IE will be set to missing; such missing data will be imputed/substituted under a Missing Not at Random (MNAR) assumption by borrowing information from the placebo arm subjects (reference-based imputation).
 - IEs leading to study discontinuation due to other reasons.
 - IEs related to the COVID-19 pandemic
 Policy strategy: Available data will be used; missing data will be imputed under a Missing at Random (MAR) assumption, borrowing information from subjects in the same treatment arm.
- Summary measure: Identification of the dose-response curve and estimation of the target dose

Statistical Methods & Analysis

The MCP-Mod methodology (Bretz 2005; Pinheiro 2014) will be employed to assess the primary objective: to investigate the dose-response relationship for different doses of MM-120 versus placebo in change from Baseline in HAM-A Total Score at Week 4. An overview of the steps for the MCP-Mod methodology is given below.

Step 1

The analysis to derive the test statistics is based on an analysis of covariance (ANCOVA) model with the change from Baseline to Week 4 for HAM-A Total Score as a response variable, treatment (placebo and all MM-120 doses), and Baseline value of HAM-A Total Score. Centers will be pooled according to country and region as appropriate and as defined in the SAP prior to unblinding.

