Model averaging will be carried out for each imputed data set, and the resulting mean efficacy estimates, and confidence intervals will be derived using the combination variance that accounts for the uncertainty of the imputed data using Rubin's combination rules. Comparisons between MM-120 doses and placebo will be simultaneously derived for the model averaged estimates together with confidence intervals reflecting the imputation procedure applied. The

model-averaging-based estimates of the mean changes from Baseline to Week 4 for HAM-A Total Score within each dose group, and the mean differences between MM-120 and placebo and their confidence intervals will then be displayed.

Target dose selection will be based on the model change from Baseline to Week 4 for HAM-A Total Score over the dose range studied.

Detailed information about the algorithms including multiple imputation will be specified in the SAP that will be finalized prior to unblinding.

The MCP-Mod analysis will be performed on the FAS population. It will also be performed on the PPS as a sensitivity analysis.

Handling of Missing/Potentially Biased Values

Missing data will be imputed using a multiple imputation approach assuming that the missingness mechanism can be retrieved from observed data. The imputation model will include the longitudinal sequence of HAM-A Total Score.

For IEs, handling will depend on the IE causing the missing or potentially biased value as follows:

- The data recorded after the IE will be imputed/substituted under an MNAR assumption by borrowing information from the placebo arm subjects (reference-based imputation) for the following:
 - For intake or change in concomitant medications/therapies that have potential confounding effects per the impact assessment; or
 - For intake of prohibited medications/therapies assessed as "Yes" per the impact assessment.
- Missing data will be imputed under a MAR assumption, borrowing information from subjects in the same treatment arm for the following:
 - For IEs leading to study discontinuation due to other reasons than the above, including IEs related to the COVID-19 pandemic.

Centers will be pooled according to country and region as appropriate and as defined in the SAP prior to unblinding.

The full detailed information about the multiple imputation algorithms will be specified in the SAP.

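### SAP 6.1.1 limits the placebo-imputed intercurrent event to medications, while the protocol estimand covers medications and therapies, and the SAP does not disclose the narrowing

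*SAP*

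**What the plan says.** Protocol 10.2.2.1 names two events before the Week 4 HAM-A that lead to placebo-based (MNAR) imputation. The first is "Intake or change in concomitant medications/therapies which have potential confounding effects per the impact assessment". The second is "Intake of prohibited medications/therapies assessed as 'Yes' per the impact assessment". The part of the same section on missing and potentially biased values repeats both, with the same scope.

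SAP 6.1.1 has one bullet for this strategy, and it begins "Concomitant/prohibited medications that meet the threshold for impact". Scores after such an event are set to missing and imputed from placebo. The SAP's other two categories are "For IEs leading to study discontinuation due to other reasons" and events related to COVID-19. For these, available data are used and missing data are imputed under MAR from the same arm. SAP 6.2.1 applies the same process to Week 8.

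On non-drug therapy, Protocol 6.10.1 states: "Subjects must also avoid starting, stopping or altering non-medicinal therapies from the time of providing informed consent until End of Study". Protocol 5.2.3 gives psychotherapy, acupuncture and hypnosis as examples. Protocol 5.2.3 and 8.1.7 have these therapies recorded from consent to End of Study. SAP 5.7 handles non-drug treatments as a class of their own, with separate coding and separate tables.

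**The concern.** The protocol leaves the imputation algorithm to the SAP, but it fixes in the estimand which events count. The SAP rule is the one that gets programmed, and it covers fewer events. The difference decides whether certain observed Week 4 and Week 8 scores are kept or replaced, so it bears on which estimand the primary and key secondary analyses address.

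A new course of psychotherapy could change a HAM-A score independently of study drug. The protocol itself expects possible functional unblinding (2.4, 8.4.5, 8.5), so it is plausible that uptake of such therapy would differ by arm. If it did, the retained scores would mix the effect of study treatment with that of another intervention. A rule on which observed scores to keep is also hard to defend when it departs from the protocol without being listed as a change.

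**Working it through.** **1. Scope side by side**

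| Element | Protocol 10.2.2.1 | SAP 6.1.1 |
|---|---|---|
| Concomitant use | medications and therapies | medications |
| Prohibited use | medications and therapies | medications |
| Condition | positive impact assessment | positive impact assessment |
| Handling | set to missing, placebo-based MNAR | set to missing, placebo-based MNAR |

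The handling and the impact condition agree. Only the scope differs.

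**2. Can medications in the SAP be read to include therapies?** Not readily. SAP 5.7 codes medications with the WHO drug dictionary and non-drug treatments with MedDRA, and tabulates them separately. Protocol 6.10 also lists medications, therapies and supplements as three things. In the Schedule of Activities (Protocol Table 2, repeated in SAP Appendix A), the concomitant-use row opens with medications and non-medicinal therapies and then shortens this to medications/therapies, the same pair of words that the estimand uses.

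**3. Trace one subject.** A subject starts psychotherapy in Week 1, stays in the study and has a Week 4 HAM-A.
- Protocol: the therapy goes to the impact assessment. If that is positive, the Week 4 score is set to missing and imputed from placebo. If not, the score stays.
- SAP, read literally: this is not a medication, not a discontinuation and not related to COVID-19. No category applies and the score is not missing, so the observed value enters the FAS analysis. The same holds at Week 8.

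**4. Is the narrowing declared?** SAP Section 8 describes the timing of the top-line analysis and does not mention the change. The SAP addendum (Section 1) says that it makes no change to the pre-planned analyses, so it does not correct the rule either.

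**5. Size**

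Inputs from the documents (Protocol 10.2.2.2, SAP Section 9): 36 per arm, maximum standardized effect 0.6, one-sided 0.05. With these inputs and the six candidate curves, a max-t simulation (critical value about 2.045) returns the plan's power table to 0.1 point: 84.5, 90.7, 91.0, 89.9, 83.2 and 85.0. The mean is 524.3/6 = 87.4%. These figures assume no intercurrent events, so the wording mismatch does not change them. They supply only the scale for the illustration.

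Assumptions, not in the documents: *k* subjects in one arm are affected, and each retained score differs from its imputed value by *D* SD, all in the same direction.

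Shift in that arm's mean = *k* × *D* / 36.
- *k* = 1, *D* = 0.3: 0.3/36 = 0.008 SD, and 0.0083/0.6 = 1.4% of the design effect.
- *k* = 2, *D* = 0.6: 1.2/36 = 0.033 SD, or 5.6%.
- *k* = 4, *D* = 1.0: 4/36 = 0.111 SD, or 18.5%.

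In HAM-A points, with an assumed difference of 5 to 10 per subject, one subject gives 5/36 = 0.14 to 10/36 = 0.28. Four subjects at 10 points give 40/36 = 1.1.

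**The case against.** **The SAP wording may be shorthand.** Protocol Table 5 has other therapies in its title but lists only drugs and substances. Protocol 8.1.7 speaks of concomitant therapies and then says that non-medicinal ones are recorded as well. On that reading, therapies in the estimand need not mean psychotherapy. This lowers certainty about intent. It does not remove the mismatch, because Protocol 6.10.1 deals with non-medicinal therapies in its own prohibited-use text and the Schedule of Activities uses the paired term to include them.

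**The per-protocol analysis offers some protection.** A therapy change departs from Protocol 5.2.3 and 6.10.1. If it is judged a major deviation affecting the endpoint, the subject leaves the PPS, on which the MCP-Mod analysis is repeated. That stands as a partial sensitivity check. It drops the subject instead of imputing the score, and it leaves the FAS result untouched.

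**Such events may be rare.** Entry requires stable non-medicinal therapy with no plan to change it, and only changes before the assessment matter. This is fair, and the documents give no rate in either direction.

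A reader might also infer more than the documents support:
- *That medication changes are lost too.* SAP 6.1.1 does not use the word change. But under SAP 5.7 a medication that ends on or after the first dose, or is ongoing, is concomitant. One whose dose changes after dosing can therefore still be rated as impactful.
- *That transcranial magnetic stimulation is an equal example.* It appears with similar procedures in exclusion 21. It is neither in Table 5 nor among the examples in 5.2.3.
- *That the protocol restricts these therapies because they affect anxiety.* It gives no such reason for them.

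**Conclusion.** The mismatch is real. The protocol's placebo-imputed event covers medications and therapies, the SAP's covers medications, and the SAP does not list the difference. Under the literal SAP rule, the observed score of a subject who starts or alters psychotherapy and remains in the study stays in the FAS primary and key secondary analyses. The protocol would have replaced it after a positive impact assessment.

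The conclusion rests on reading therapies to include non-medicinal ones, which is the better-supported reading but not the only one. The stronger inference, that the primary result is biased, is not supported. The protocol itself would keep a score judged not impactful, differential uptake by arm is conjecture, and no direction can be assigned. The illustrated range of 1.4% to 18.5% of the design effect depends wholly on assumed counts and differences. The true effect could be nil.

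**What to change.** Reword the SAP 6.1.1 bullet to the protocol's scope, for example: *Intake of or change in concomitant medications or therapies, or intake of prohibited medications or therapies, including non-medicinal therapies in each case, assessed as impact = Yes, is the intercurrent event; later observations are set to missing and imputed under MNAR from the placebo arm.* State that the impact assessment covers the non-drug treatment records for both Week 4 and Week 8.

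The SAP addendum records that its analyses were added after unblinded review of the primary endpoint, so rewording alone is no longer enough. Have reviewers blinded to treatment assignment apply the impact assessment to the non-drug treatment records. Disclose the departure, and report the protocol-defined analysis alongside the SAP analysis.

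The cost is one SAP sentence, one more dataset in the impact review, and a rerun of the primary and key secondary analyses. No new data are needed. The downside is small: a few more scores may be imputed.
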